#### 14.5 Reporting of SAEs, Pregnancy, and Other Events of Interest

#### 14.5.1 Reporting of SAEs

All serious adverse events (SAEs), irrespective of relationship to study treatment, must be reported on a completed SAE form by email ([contact]) or [contact]) as soon as possible within **24 hours since awareness of the SAE**. Serious adverse events, regardless of causality assessment, must be collected from the signature of the ICF by the patient through the termination visit and for 28 days following study drug discontinuation, whichever is longer. All SAEs must be followed to resolution, or if resolution is unlikely, to stabilization. Any SAE judged by the investigator to be related to the study treatment should be reported to the sponsor

Page 63 of 88 Date: April 04th, 2016

regardless of the length of time that has passed since study completion. Deaths and life-threatening events should be reported immediately by telephone. The immediate report should be followed-up within 24 hours since awareness of such information by emailing or faxing the completed SAE form. The detailed contact information for reporting of SAEs is provided in the Investigator File.

For urgent safety issues, please ensure all appropriate medical care is administered to the subject and contact the appropriate study team member listed in the Investigator File. It is very important that the SAE report form be filled out as completely as possible at the time of the initial report. This includes the investigator's assessment of causality.

Any follow-up information received on SAEs should be forwarded within 24 hours of its receipt. If the follow-up information changes the investigator's assessment of causality, this should also be noted on the follow-up SAE form.

The investigator should notify his/her EC of the occurrence of the SAE, in writing, in accordance with local requirements. A copy of this communication must be forwarded to the CRO monitor and filed in the Trial Master File.

## 14.5.2 Reporting of Pregnancy

Any pregnancy where the estimated date of conception occurs either prior to the study termination visit or within 28 days of the last study treatment must be reported. If an adverse outcome of a pregnancy is suspected to be related to study drug exposure, this should be reported regardless of the length of time that has passed since the exposure to study treatment.

An induced abortion or a spontaneous abortion is considered to be an SAE and should be reported in the same timeframe and in the same format as all other SAEs. Pregnancies must be reported within 24 hours since awareness of it by [contact]) or email ([contact]). The contact information for the reporting of pregnancies is provided in the Investigator File. The Pregnancy Report Form must be used for reporting. All pregnancies must be followed to outcome. The outcome of the pregnancy must be reported within 24 hours since awareness of it.

A subject who becomes pregnant must be withdrawn from the study.

#### 14.5.3 Reporting of Overdose

Study drug overdose is the accidental or intentional use of the drug in the amount higher than the dose being studied. Any study drug overdose during the study should be noted on the study medication CRF.

All AEs associated with an overdose should both be entered on the Adverse Event CRF and reported using the procedures detailed in Reporting of SAEs even if the events do not meet serious criteria. If the AE associated with an overdose does not meet serious criteria, it must still be

Page 64 of 88 Date: April 04th, 2016

reported using the SAE form and in an expedited manner but should be noted as non-serious on the SAE form and the Adverse Event CRF.

## 14.6 Expedited reporting

The sponsor must inform investigators (or, as regionally required, the head of the medical institution) and regulatory authorities of reportable events, in compliance with applicable regulatory requirements, on an expedited basis (i.e., within specific timeframes). For this reason, it is imperative that investigational sites provide complete SAE information in the manner described above.

### 14.7 Regulatory reporting of adverse events

Adverse events will be reported to regulatory authorities in compliance with local and regional law and established guidance by the sponsor, or a third party acting on behalf of the sponsor. The format of these reports will be dictated by the local and regional requirements and will comply with the European Clinical Trial Directive 2005/28/EC. All suspected unexpected serious adverse reactions (SUSARs) will be reported as required to the Competent Authorities of all involved European member states.

### 14.8 Treatment Emergent Adverse Event

TEAE is defined as any event not present prior to the initiation of the study drug or any event already present that worsens in either intensity or frequency following exposure to the study drug. TEAE provides more relevant and useful information than a general AE to the investigators. Therefore, most AE tables in statistical reports should be based on TEAE. In this sense, any unfavorable and unintended sign prior to dosing 3 but not worsening during the treatment will be automatically excluded from the analysis. The programming practice to code a TEAE is comparing AEs onset date/time and first study drug administration date/time. If the AE has the same intensity before and after the first drug administration, then it is not counted as TEAE. Note that a TEAE is not necessarily a drug related AE.

### 14.8.1 Management of hypertension

Hypertension is a recognized side-effect of treatment with drugs inhibiting VEGF signaling. Investigators should therefore ensure that subjects enrolled to receive treatment with lenvatinib have BP < 150/90 mmHg at the time of study entry and, if known to be hypertensive, are on antihypertensive therapy before they start treatment with lenvatinib. The early detection and effective management of hypertension are important to minimize the need for lenvatinib dose interruptions and reductions. Antihypertensive agents should be started as soon as the BP is confirmed to be ≥ 140/90 mmHg on 3 measurements performed every 5 minutes after the first measurement, and a last measurement performed in an hour. The choice of antihypertensive EudraCT no.: 2015-001467-39

Page 65 of 88 Date: April 04th, 2016

treatment should be individualized to the subject's clinical circumstances and follow standard medical practice. For previously normotensive subjects, monotherapy with one of the classes of anti-hypertensives should be started when  $BP \ge 140/90$  mmHg is first observed. For those subjects already on antihypertensive medication, the dose of the current agent may be increased, if appropriate, or one or more agents of a different class of antihypertensive should be added. For subjects with hypertension and proteinuria, treatment with an angiotensin-converting enzyme inhibitor or angiotensin-II receptor antagonist is preferred.

Study drug should be withheld in any instances where a subject is at imminent risk to develop a hypertensive crisis or has significant risk factors for severe complications of uncontrolled hypertension (e.g.,  $BP \ge 160/100$  mmHg, significant risk factors for cardiac disease, intracerebral hemorrhage, or other significant co-morbidities). Once the blood pressure is controlled, study drug should be resumed as described below.

The following guidelines should be followed for the management of systolic BP  $\geq$  140 mmHg to <160 mmgHg or diastolic BP  $\geq$  90 mmHg to 100mmgHg confirmed on repeat measurements after an hour:

- Continue study drug and institute antihypertensive therapy for subjects not already receiving this.
- For those subjects already on antihypertensive medication, the dose of the current agent may be increased, if appropriate, or one or more agents of a different class of antihypertensive should be added.
- If systolic BP ≥ 160 mmHg or diastolic BP ≥ 100 mmHg persists despite maximal antihypertensive therapy, then study drug administration should be interrupted and restarted at a dose of 20 mg once daily when BP ≤ 150/95 mmHg and the patient has received a stable dose of antihypertensive drugs within at least 48 hours. (Refer to Table 3 for instruction regarding duration of the interruption of drug administration and decision of reintroduction)
  - o If systolic BP ≥ 160 mmHg or diastolic BP ≥ 100 mmHg recurs on the 20-mg once daily dose despite optimal management of hypertension with antihypertensive medications (either by dose increase or the addition of a different class of antihypertensive), then study drug administration should be interrupted and restarted at a dose of 14 mg once daily when BP ≤ 150/95 mmHg.
  - o If systolic BP ≥ 160 mmHg or diastolic BP ≥ 100 mmHg recurs on the 14-mg once daily dose despite optimal management of hypertension with antihypertensive medications (either by dose increase or the addition of a different class of antihypertensive), then study drug administration should be interrupted and restarted at a dose of 10 mg once daily when BP ≤ 150/95 mmHg.

o Additional dose reduction should be discussed with the sponsor.

The following guidelines should be followed for the management of Grade 4 hypertension (life-threatening consequences):

- Institute appropriate medical management.
- Discontinue of study drug

A summary table of treatment for hypertension is shown below.

Table 6.- Treatment for hypertension

Level of blood pressure (BP)	Recommended action					
Systolic BP ≥140mmHg to <160 mmHg or Diastolic BP ≥90 mmHg to <100 mmHg	Continue with treatment with lenvatinib and start antihypertensive treatment, if it has not been administered yet OR Continue with treatment with lenvatinib and increase the dose of current antihypertensive drug or start and additional antihypertensive treatment					
Systolic BP ≥160 mmHg or Diastolic BP ≥100 mmHg despite the administration of a treatment optimal antihypertensive	
 
Discontinue the administration of lenvatinib
 
If systolic BP is ≤150 mmHg, diastolic BP is ≤95 mmHg and the patient has received a stable dose of antihypertensive medication during at least 48 hours, resume the administration of lenvatinib to a reduced dose.
 
					
Life-threatening consequences (malignant hypertension, neurological damage or hypertensive crisis)	An immediate action is required. Discontinue treatment with lenvatinib and start appropriate medical treatment					

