## 11.7 Dose reduction and interruption instructions

In case of treatment related toxicity please follow the dose reduction and interruption instructions provided in Table 3.

For details about the instructions for dose reduction and interruption in case of hypertension and proteinuria, please see Sections 14.8.1 and 14.8.2 of the protocol. In case of doubts regarding other specific cases, see the study reference information (Investigator Brochure and/or Summary of Product Characteristics) provided by the study sponsor.

Table 3. - Dose reduction and interruption instructions

Freatment-Related Toxicity**,b	During Therapy	Adjusted Dose
	Grade 1	
	Continue treatment	No change
		• •
	Intolerable Grade 2°	
First occurrence	Interrupt until resolved to Grade 0-1 or baseline	No change
Second occurrence (same toxicity or new toxicity)	Interrupt until resolved to Grade 0-1 or baseline	20 mg orally once a day
Third occurrence (same toxicity or new toxicity)	Interrupt until resolved to Grade 0-1 or baseline	14 mg orally once a day
Fourth occurrence (same toxicity or new toxicity)	Interrupt until resolved to Grade 0-1 or baseline	10 mg orally once a day
Fifth occurrence (same toxicity or new toxicity)	Interrupt until resolved to Grade 0-1 or baseline	Discuss with sponsor
	Grade 3	
First occurrence	Interrupt until resolved to Grade 0-1 or baseline	20 mg orally once a day
Second occurrence (same toxicity or new toxicity)	Interrupt until resolved to Grade 0-1 or baseline	14 mg orally once a day
Third occurrence (same toxicity or new toxicity)	Interrupt until resolved to Grade 0-1 or baseline	10 mg orally once a day
Fourth occurrence (same toxicity or new toxicity)	Interrupt until resolved to Grade 0-1 or baseline	Discuss with sponsor

Note: For grading see CTCAE v.4.03 (Appendix IV). Collect all CTC grades of AE, decreasing and increasing grade.

- a) A delay of study treatment for more than 28 days (due to treatment-related toxicities) will require a discussion with the sponsor before treatment can be resumed
- b) Initiate optimal medical management for nausea, vomiting, and/or diarrhea prior to any study treatment interruption or dose reduction
- c) Applicable only to Grade 2 toxicities judged by the subject and physician to be intolerable.
- d) Excluding laboratory abnormalities judged to be non-life threatening, in which case manage as Grade 3.

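### The first hypertension step in Protocol 14.8.1 restarts lenvatinib at a fixed 20 mg, which is no reduction, or an increase, for a patient already reduced to 20, 14 or 10 mg

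*Protocol*

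**What the plan says.** Section 11.5 starts every patient on 24 mg daily. Section 11.7 and Table 3 then lower the dose to 20, 14 and 10 mg for treatment-related toxicity, counting repeat and new toxicities alike. For hypertension, 11.7 refers the reader elsewhere: "For details about the instructions for dose reduction and interruption in case of hypertension and proteinuria, please see Sections 14.8.1".

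Section 14.8.1 tells sites that "Once the blood pressure is controlled, study drug should be resumed as described below". The steps that follow are:

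- **First step.** If systolic pressure of at least 160 mmHg or diastolic of at least 100 mmHg persists on maximal antihypertensive treatment, "study drug administration should be interrupted and restarted at a dose of 20 mg once daily when BP ≤ 150/95 mmHg", provided antihypertensive doses have been stable for at least 48 hours. The dose at onset is not mentioned.
- **Second step**, to 14 mg, if the pressure "recurs on the 20-mg once daily dose despite optimal management of hypertension".
- **Third step**, to 10 mg, if it "recurs on the 14-mg once daily dose despite optimal management of hypertension".
- **After that**, any additional reduction is discussed with the sponsor.

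The first step also refers back to Table 3: "Refer to Table 3 for instruction regarding duration of the interruption of drug administration and decision of reintroduction".

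The section closes with Table 6 (Treatment for hypertension), introduced by "A summary table of treatment for hypertension is shown below". For the same blood pressure level and the same restart conditions, the table says to "resume the administration of lenvatinib to a reduced dose". It gives no figure in mg.

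**The concern.** The second and third steps are tied to the dose at which the problem comes back. The first step is not. It is written as if every patient reaching it were still on 24 mg, but Table 3 allows a patient to be on a lower dose already, because of some other toxicity, when hypertension first forces an interruption. For that patient the first step and Table 6 disagree.

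The patient concerned has blood pressure that maximal treatment did not control. A site that follows the written step would restart the drug that raises blood pressure at the same or a higher dose. A site that follows Table 6 would go down, but would have to find the dose elsewhere. This is a matter of safety and of consistency between sites. It does not touch the primary endpoint, the sample size or any analysis.

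**Working it through.** **Inputs.** Starting dose 24 mg (11.5). Dose levels 24, 20, 14 and 10 mg, then discussion with the sponsor (Table 3; the steps in 14.8.1 use the same levels). First-step restart dose 20 mg, unconditional (14.8.1). Restart at a reduced dose (Table 6).

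**1. The plan's own figure.** 20 mg is one level below 24 mg: (20 − 24)/24 = −16.7%. Text and Table 6 agree here, so the step is right for a patient still on the starting dose.

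**2. Whether a patient can be below 24 mg beforehand.** Using rows within one grade block of Table 3:

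| Dose reached | Grade 3 occurrences needed | Intolerable Grade 2 occurrences needed |
|---|---|---|
| 20 mg | 1 | 2 |
| 14 mg | 2 | 3 |
| 10 mg | 3 | 4 |

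Section 5.2.2 lists diarrhea, fatigue, stomatitis, proteinuria and others among the main side effects, so an earlier reduction for another toxicity is plausible.

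**3. The first step applied at each dose.** Change = (20 − dose at onset)/dose at onset.

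| Dose at onset | Literal restart | Change | Reduced, as in Table 6? | One level down | Literal minus one level down |
|---|---|---|---|---|---|
| 24 mg | 20 mg | −4 mg (−16.7%) | yes | 20 mg | 0 |
| 20 mg | 20 mg | 0 (0%) | no | 14 mg | +6 mg/day |
| 14 mg | 20 mg | +6 mg (+42.9%) | no | 10 mg | +10 mg/day |
| 10 mg | 20 mg | +10 mg (+100%) | no | sponsor | not defined |

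The step agrees with Table 6 only in the first row.

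**4. Whether the later steps catch these patients.** They require pressure that recurs on 20 or 14 mg. A patient with an earlier episode at this level, including one controlled without an interruption, meets that condition and is handled correctly. A patient whose first such episode occurs at a reduced dose does not meet it as worded. No step names 10 mg as the dose at onset.

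**5. Whether Table 3 supplies the dose.** Section 11.7 sends hypertension dosing to 14.8.1. The reference back to Table 3 names the length of the interruption and the decision to reintroduce, not the dose. Section 14.8.2 differs: for proteinuria it sends management of drug administration to Table 3 outright. For a first episode, the only mg figure in 14.8.1 is therefore 20. Nothing in the protocol forbids raising a dose that has been reduced.

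**The case against.** The strongest reply is that the protocol as a whole plainly means the dose to go down. Section 11.7 opens by applying Table 3 to all treatment-related toxicity, and that table only descends. Section 14.8.1 can be read as adding detail to Table 3 rather than replacing it. A site sent to Table 3 for the decision to reintroduce would see its adjusted-dose column. If the condition of recurrence is read loosely, a physician with an uncontrolled patient on 14 mg has a step naming 14 mg that leads to 10 mg, and a patient on 10 mg falls under the line on discussion with the sponsor. An increase would require a site to overlook all of this as well as Table 6. The group is narrow, restart needs a pressure of 150/95 mmHg or below, and 20 mg is still below the starting dose.

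Much of this stands. The intent can be inferred, the cross-references point to 14.8.1 as a whole and not to its first bullet, and the group is small. What does not follow is that the text is sound. Each of these readings asks the site to set aside the one explicit dose written for the situation, or to ignore the word limiting the later steps to recurrence. The blood pressure and 48-hour conditions limit the risk of restarting, but they do not correct the dose.

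**Conclusion.** The point holds. As written, the first step of 14.8.1 gives a wrong dose for a first hypertension interruption in a patient already reduced for another toxicity: no reduction at 20 mg, +43% at 14 mg and +100% at 10 mg, against the reduced dose called for in Table 6. This is more than missing detail, because a stated rule contradicts its own summary table.

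The conclusion rests on reading the first step literally and on taking recurrence to presuppose an earlier episode at this blood pressure level. The number of patients affected is unknown, since the documents give no event frequencies. Patients still on 24 mg, and those with recurrent hypertension, are not affected. It should be fixed on safety grounds; no consequence for the response rate is claimed.

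**What to change.** Change only the first step in 14.8.1, so that it reads along these lines:

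> Restart one dose level below the dose at onset (24 to 20, 20 to 14, 14 to 10 mg; below 10 mg discuss with the sponsor). No restart may exceed the dose at onset.

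The blood pressure and 48-hour conditions stay. The two later steps, Table 6 and Table 3 need no change: the new wording satisfies Table 6 at 24, 20 and 14 mg, sends 10 mg to the sponsor, and matches the 20, 14, 10 mg sequence of the Grade 3 rows in Table 3.

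The cost is a wording amendment to one bullet and a letter to sites. Because it affects subject safety, Section 17.1 requires submission to the health authorities and ethics committee approval, at about 25 planned sites in four countries (Section 4.7). It adds no patients, visits or procedures.

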### 14.8.2 Management of Proteinuria

Regular assessment for proteinuria should be conducted as detailed in the schedule of visits and procedures (table 4). Guidelines for assessment and management of proteinuria are summarized as follows:

• Initial episode of proteinuria: if proteinuria ≥ 2+ is detected on urinalysis, study drug will be continued and a 24-hour urine collection for total protein will be obtained as soon as possible within 72 hours to verify the grade of proteinuria. Grading according to the National Cancer Institute's (NCI) Common Terminology Criteria for Adverse Events (CTCAE v4.03, Appendix IV) will be based on the 24-hour urinary protein result. Management of study drug

administration will be based on the grade of proteinuria according to the dose reduction and interruption instructions provided in Table 3.

 Urinalysis should be performed every 4 weeks subsequent to cycle 2 during the treatment phase and any increases in the level of proteinuria on urinalysis up to 3+ needs to be confirmed with a 24-hour urinary protein test which will be assessed and graded according to the dose reduction and interruption instructions provided in Table 3.

### 15. Data quality assurance

This study will be organized, performed, and reported in compliance with the protocol, standard operating practices (SOPs), working practice documents, and applicable regulations and guidelines. Site visit audits will be made periodically by the sponsor's or CRO's qualified compliance auditing team, which is an independent function from the study conduct team.

#### 15.1 Data Collection

Data required by the protocol are collected on an electronic Case Report Form (eCRF) and entered into a validated data management system which is compliant to all regulatory requirements. As defined by ICH Guidelines, 'the Case Report Form (CRF) is a printed, optical, or electronic document designed to record all of the protocol required information to be reported to the sponsor on each trial subject'. In this study, CRF should refer to electronic data collection form. Data collected on the CRF must follow the instructions described in the CRF Completion Guidelines. The Investigator has ultimate responsibility for the collection and reporting of all clinical, safety and laboratory data entered on the CRF.

The primary objective of the study will be ORR by central radiology review. Images of tumor assessments will be anonymized correctly identified with trial number patient (code dissociated) and send to Vall d'Hebron University Hospital for revision by an independent experienced radiologist.

#### 15.2 Clinical Data Management

All software applications used in the collection and validation of data must be properly validated following standard computer system validation and must be compliant to all regulatory requirements.

The Data Management Plan (DMP) defines and documents the procedures necessary to ensure data quality. These activities must be followed to ensure data are properly entered, validated, coded, integrated, reconciled and reviewed.

Data cut-off for the study primary analysis will take place after the last patient enrolled in the study has performed the second tumor assessment (week 12 after the first dose of study drug) given that the first assessment will be performed 6 weeks after the first dose). Subsequent tumor

Page 68 of 88 Date: April 04th, 2016

assessments will be performed starting on week 12 every 12 weeks until documentation of disease progression or start of another anticancer therapy.

